3.5.5 Statistical Methods

3.5.5.1 Efficacy Analysis

Part A: Patients' best tumor response along with tumor type and other baseline characteristics will be listed.

Part B ipilimumab-naïve treated at 10 mg/kg enrolled through Amendment 4: Overall response rate (RR) and disease control rate (DCR) will be used as endpoints for efficacy assessment for internal decision purpose. A 95% confidence interval along with a one-sided p-value for testing the null hypothesis based on the binomial distribution will be provided for each for the two primary endpoints: overall RR and overall DCR. Similar analyses will be provided for interim analyses of RR and DCR at week 12. Exploratory analyses will be conducted to compare the PFS rate at 6-month and OS rate at 1-year with historical control as well as with the recent ipilimumab data adjusted with baseline factors such as ECOG [75].

RR will be the primary endpoint for efficacy assessment in all populations. The primary assessment is based on RECIST 1.1 by blinded central reviewers, and the secondary assessment is based on irRC by investigators. A 95% confidence interval for RR will be provided for each population and by dose/schedule as applicable. Although DCR is not the primary endpoint, similar analyses will also be provided. In addition, Kaplan-Meier plots and descriptive statistics of progression-free-survival (PFS) and overall survival (OS) will be provided. Further, in order to adjust for inadequate follow-up, Kaplan-Meier plot and descriptive statistics of time-to-response will be provided whereas the Kaplan-Meier estimate of cumulative response rate at the longest follow-up time-point will serve as an estimate of the overall response rate. Response rate based on patients with at least 28 weeks of follow-up will also be provided as an approximate of the overall response rate. Descriptive statistics will also be provided for analysis of response duration and tumor volumetric change. Between-treatment comparisons will be conducted for all efficacy endpoints as appropriate to investigate the dose/schedule difference.

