3.2.5.4.7 Duration of Follow-up

All patients have to be followed for at least 30 days after their last dose of study drug or until initiation of a new anti-cancer treatment, whichever occurs first.

Patients who are discontinued from the study due to an unacceptable drug related adverse event will be followed until the resolution of the AE to Grade 0-1 or stabilization or until beginning of a new therapy for their cancer, whichever occurs first.

In Parts A, B, C, D and F, patients who discontinued study therapy without documented disease progression, monitoring of their disease status by radiologic imaging should continue following the guidelines described in the Study Flow Chart (Section 1.7;

Parts B, C, D and F: Follow-Up). Disease monitoring should continue (1) until start of a new anti-cancer treatment (information of the new cancer therapy will be collected), (2) until documented disease progression, or (3) until death, whichever occurs first.

For patients in Parts A, B, C, D and F who achieve a SD or PR or CR, and who stop study treatment, the mandatory Safety Follow-up Visit should be performed approximately 30 days after the last infusion of study medication. Procedures and assessments performed at the Safety Follow-up Visit should follow the respective guidelines described in the Study Flow Chart as appropriate. Beyond the Safety Follow-up Visit, patients will continue to be monitored for adverse events and followed per the standard follow-up period as described in the Study Flow Chart (Section 1.7). However, CR, SD, PR patients will not exit the standard follow-up, and will continue to return to the clinic every 3 months for the duration of the study following the Follow-up flow chart.

Subjects who are eligible to receive retreatment with pembrolizumab (MK-3475) according to the criteria in Section 3.2.5.4.9 will move from the Follow-up Phase to the Second Course Phase when they experience disease progression.

Patients will be followed long-term for survival as described in the Study Flow Chart (Section 1.7; Parts B, C, D, and F: Follow-up).

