The irRC is a recently published set of guidelines proposed for immunotherapies in solid tumors [18]. The guidelines were prompted mostly by the clinical observation that some patients can have a temporary increase in existing tumor lesions or the transient occurrence of a new lesion after start of immunotherapy, while ultimately experiencing treatment benefit in form of an objective disease response or long lasting disease stabilization. Analysis of more than 200 patients with MEL who had received study therapy with ipilimumab showed approximately 10% of patients falling into that category. This subgroup of patients had an overall survival that was comparable to that in patients who had a CR, PR or SD on the basis of traditional WHO criteria [18].

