If imaging shows PD, it is at the discretion of the investigator to keep a patient on study treatment or to stop study treatment until repeat imaging will be repeated approximately 4 to 6 weeks later, in order to confirm PD. Patients that are deemed clinically unstable are not required to have repeat imaging for confirmation. This decision will be based on clinical judgment of a patient's overall clinical condition, including performance status, clinical symptoms, and laboratory data. Section 2.4.1 lists the criteria for determining clinical stability. If repeat imaging shows an objective response or stable disease, treatment with pembrolizumab (MK-3475) will continue/ resume per imaging schedule. If repeat imaging confirms PD, patients will be discontinued from study therapy or permitted to continue treatment if the investigator believes patient is deriving benefit with sponsor consultation. This clinical judgment decision by the site should be based on the subject's overall clinical condition, including the following parameters:

- 1) Absence of symptoms and signs indicating clinically significant progression of disease, including worsening of laboratory values
- 2) No decline in ECOG performance status
- 3) Absence of rapid progression of disease
- 4) Absence of progressive tumor at critical anatomical sites (e.g., cord compression) requiring urgent alternative medical intervention

The same paradigm for confirmatory scans of response (4 weeks after the initial finding) or progression of disease (4-6 weeks after the initial finding) is applicable to subsequent planned scanning intervals

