3.5.3 Analysis Endpoints

3.5.3.1 Efficacy Endpoints

RR and DCR will serve as primary efficacy endpoints only for the ipilimumab-naïve population treated at 10 mg/kg in Part B enrolled through Amendment 4 for internal decision purposes, and the study in this population is considered positive (i.e., demonstration of proof-of-concept in this population) if the outcome in either endpoint is positive. The recently published immune-related response criteria (irRC) as assessed by investigators will be applied as primary measure for assessment of tumor response [18]. RR and DCR will be also assessed based on RECIST 1.1 by blinded central reviewers as supportive analyses. Interim analyses will be based on RR and DCR at Week 12. Confirmation is required for final analysis of RR, but not for the interim analyses. Secondary efficacy endpoints for the above population will include duration of response, progression-free survival (PFS) and overall survival (OS). Response duration will be only determined for confirmed responses and is defined as the time from first documentation of response to first documentation of disease progression or death. PFS will be measured from start of treatment to documentation of definitive disease progression or death due to any cause, whichever occurs first. OS is defined as time from treatment initiation to death due to any cause.

The primary endpoint is RR to further demonstrate the anti-tumor activity of pembrolizumab (MK-3475) in all populations except as noted above. The primary measure for assessment of tumor response is based on RECIST 1.1 by blinded central reviewers and the secondary measure is based on irRC by investigators. DCR, response duration and PFS based on both irRC and RECIST 1.1, and OS will serve as secondary endpoints.

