Kendall's tau statistic along with a one-sided p-value will be provided for testing the concordance between maximum total tumor volume reduction (%) produced by pembrolizumab (MK-3475) and PD-L1 expression levels in tumor tissue [20]. Kendall's tau statistic is rank based. For the supportive analysis, those without a post-treatment disease assessment (presumably mainly due to discontinuation before week 12) will be assigned a lower rank (equivalent to less tumor reduction) than those with a post-treatment disease assessment. They will further be ranked by category of reasons for discontinuation (death, disease progression by RECIST 1.1 per central review and other reasons) in ascending order, and among each category they will be ranked by time to

discontinuation, the earlier the lower. Supportive analysis will be performed assessing the concordance between response by RECIST 1.1 per central review and PD-L1 expression.

Receiver operating characteristic (ROC) analysis will be generated for each scoring system. The cutoff point will be chosen by statistical estimation of Youden Index assisted with visual inspection from the ROC. In addition, the following two confounding categorical variables will be evaluated to determine whether or not they can be used to further improve the scoring system: “stroma pattern” (presence or absence of a band mononuclear inflammatory cells expressing PD-L1, in the stroma adjacent to tumor nests) and “dendritic pattern” (presence or absence of a lattice of dendritic cells expressing PD-L1, within tumor nests). Once the final scoring system and cutoff point is chosen, it will be documented before validation can be conducted.

Validation

Tumor samples from patients in the validation sets will be sent to a third party contract research organization (CRO) for re-identification. The CRO will remove old identifying information from each sample and replace it with a new identifier. The samples will then be sent to the clinical laboratory sites for analysis. Thus, both Merck and the laboratories will be blinded to the linkage between PD-L1 test result and the clinical outcome. The third-party CRO will release the key containing the old versus new identifiers to Merck only after database lock.

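### Time-to-response has no rule for patients who progress, die or start new therapy without responding; if they are censored, the supplementary Kaplan-Meier response rate is too high

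*Combined protocol and SAP*

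**What the plan says.** Section 3.5.5.1 makes the response rate (RR) with a 95% confidence interval the main efficacy analysis, in the Full Analysis Set (FAS, Section 3.5.4.1). It then adds that "in order to adjust for inadequate follow-up, Kaplan-Meier plot and descriptive statistics of time-to-response will be provided", and that "the Kaplan-Meier estimate of cumulative response rate at the longest follow-up time-point will serve as an estimate of the overall response rate". Section 2.7.1 repeats this. A further supplementary rate follows: "Response rate based on patients with at least 28 weeks of follow-up will also be provided as an approximate of the overall response rate".

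Section 3.5.3.1 defines response duration and overall survival, and for progression-free survival it says "PFS will be measured from start of treatment to documentation of definitive disease progression or death due to any cause, whichever occurs first". Time-to-response gets no such definition. No section states when a patient without a response leaves the risk set, and no competing-risk method is named. The opening of Section 3.5 rules out a separate SAP, so the rule cannot be expected elsewhere.

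Two nearby rules do not fill the gap:

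- Section 3.5.5.4 says "those without a post-treatment disease assessment (presumably mainly due to discontinuation before week 12) will be assigned a lower rank", but this ranks patients for Kendall's tau in the biomarker analysis.
- Section 3.2.5.4.7 says that for "patients who discontinued study therapy without documented disease progression, monitoring of their disease status by radiologic imaging should continue" up to certain events. That is an imaging instruction for one group of patients, not a censoring rule.

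**The concern.** Kaplan-Meier treats a censored patient as someone who would go on to respond at the same rate as those still under observation. That is reasonable for a patient whose follow-up is still running at data cutoff. It is not reasonable for one who has died, moved to another therapy or, under RECIST 1.1, progressed without responding. Censoring such patients shrinks the denominator for later responses, so one minus Kaplan-Meier lies at or above the proportion who actually respond.

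The figure is presented as an estimate of the primary endpoint, beside the crude RR, to correct an understatement caused by short follow-up. Under one permissible reading the correction can overshoot by more than the shortfall it is meant to repair, and a reader of a data cut with short follow-up would see an optimistic rate.

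**Working it through.** The documents state no value for this estimate, so there is no figure of theirs to reproduce. All event timings below are assumptions.

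**1. Worked life table.** Take 100 patients with complete follow-up and 14, 4 and 2 responses at scans 1 to 3, so the true RR is 20%. At each scan responders are counted before progressors leave.

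- Progressors censored, 40 after scan 1 and 14 after scan 2: 1 − (86/100)(42/46)(26/28) = 27.1%.
- Progressors censored, 20 then 10: 1 − (86/100)(62/66)(50/52) = 22.3%.
- All 20 responses at scan 1: 1 − 80/100 = 20.0%.
- Progressors kept at risk: 1 − (86/100)(82/86)(80/82) = 20.0%.
- Aalen-Johansen, first pattern: 14/100 + (46/100)(4/46) + (28/100)(2/28) = 20.0%.
- Aalen-Johansen, second pattern: 14/100 + (66/100)(4/66) + (52/100)(2/52) = 20.0%.

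**2. How the size depends on timing.** Let r_k and p_k be the probabilities of response and of progression at scan k among patients still event-free, and let e be the fraction leaving before scan 1.

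- Limit of the censored Kaplan-Meier figure: 1 − ∏(1 − r_k).
- True RR: (1 − e) Σ r_k ∏_{j<k}(1 − r_j − p_j).

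For the first row of the table:

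- Kaplan-Meier = 1 − 0.86 × 0.93 × 0.95 × 0.98 = 0.2554.
- True = 0.14 + 0.56 × 0.07 + 0.56 × 0.68 × 0.05 + 0.56 × 0.68 × 0.75 × 0.02 = 0.2040.

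| r_k, scans 1–4 | p_k, scans 1–4 | e | True % | Censored KM % | Excess, points |
|---|---|---|---|---|---|
| 0.14/0.07/0.05/0.02 | 0.30/0.25/0.20/0.20 | 0 | 20.40 | 25.54 | 5.14 |
| 0.14/0.07/0.05/0.02 | 0.45/0.35/0.25/0.20 | 10% | 16.55 | 25.54 | 8.99 |
| 0.14/0.07/0.05/0.02 | 0.15/0.125/0.10/0.10 | 0 | 22.80 | 25.54 | 2.74 |
| 0.17/0.03/0.02/0.01 | 0.30/0.25/0.20/0.20 | 0 | 19.65 | 21.89 | 2.24 |
| 0.18/0.02/0.01/0 | 0.30/0.25/0.20/0.20 | 0 | 19.42 | 20.44 | 1.02 |
| 0.20/0/0/0 | 0.30/0.25/0.20/0.20 | 0 | 20.00 | 20.00 | 0.00 |
| 0.20/0/0/0 | 0.30/0.25/0.20/0.20 | 10% | 18.00 | 20.00 | 2.00 |

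**3. Staggered entry.** A simulation used entry uniform over 48 weeks, cutoff 13 weeks after last entry, four scans and 2,000 runs per setting. Response probabilities were as in the first two rows (or 0.12 at scan 1), with either progression pattern and e = 0, 5 or 10%. Arm sizes come from Section 2.4.1: 168 (Part F-2 Q3W, simulated with 9-weekly scans) and 115 (Part B under Amendment 07, with 12-weekly scans).

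- Censored Kaplan-Meier: 5.1 to 9.0 points too high.
- Crude RR: 0.7 to 1.3 points too low (9-weekly) and 1.3 to 2.3 points too low (12-weekly).
- Aalen-Johansen, or non-responders kept at risk: within 0.1 point.
- With 5% true loss to follow-up per scan interval: Aalen-Johansen within 0.2 point, kept at risk 1.0 to 1.6 points low.

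**4. Other response levels.** A life table with a true RR of 30% (responses 18, 7, 3, 2; exits 25, 12, 6, 5) gives 1 − (82/100)(50/57)(35/38)(27/29) = 38.3%. A separate simulation let non-responders exit at a median of 12 to 36 weeks. Censoring then gave 12–27%, 18–37% and 35–60% for true rates of 10%, 15% and 30%; keeping them at risk gave 9.6–10.1%, 14.6–15.2% and 28.6–30.1%.

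**5. irRC.** Here a first progression does not end the chance of response. Section 3.3.1.3 says "If repeat imaging shows an objective response or stable disease, treatment with pembrolizumab (MK-3475) will continue/ resume per imaging schedule". On temporary increases before benefit, Section 3.3.1.1 reports "Analysis of more than 200 patients with MEL who had received study therapy with ipilimumab showed approximately 10% of patients falling into that category". If 5% of first progressors respond at the next scan, Aalen-Johansen with first progression as a competing event is 2.3 to 3.5 points low.

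**The case against.** The plan does not say that these patients will be censored. Its one textual clue, that the analysis exists to adjust for follow-up, suits a reading in which only unfinished follow-up is censored, and that reading has no bias. This stands: a reader might infer that the plan as written inflates the response rate, and the documents do not support that. Nor does Section 3.2.5.4.7 imply censoring, since it concerns imaging in patients who stopped therapy without progression. What remains is that two readings give different estimates of the primary endpoint and nothing chooses between them.

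A reader might also infer that the efficacy conclusions are at risk. They are not. The crude FAS RR with its confidence interval comes first, no planned decision uses the Kaplan-Meier figure, and the figures would appear together. Enrollment is complete (Section 1.5) and central imaging review ended with Amendment 10 (Section 3.3.1), so much of the setting for this device has passed.

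The 5-to-9-point range should not be read as general. More front-loaded responses or slower progression bring it down to 1 to 3 points. The simulated rates lie below the 30% versus 50% that Section 3.5.7 plans for the 230-patient Part B cohort. The crude shortfall there falls to 0.3 to 0.7 points if cutoff comes 26 weeks after last entry, nearer the six months on treatment in Section 3.2.5.6. These limits are accepted.

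**Conclusion.** The concern holds conditionally. The handling of patients who progress, die or start new therapy without responding is missing, and the direction of error under censoring is a mathematical property of the estimator. For a true RR near 20% the excess is illustratively about 1 to 9 points. It is zero if all responses come at the first scan and nobody leaves before it, and larger under harsher exit assumptions. These sizes rest wholly on assumed timings. The crude FAS RR, its 95% confidence interval, the binomial tests and the success bars in Section 3.5.7 are untouched. The point is worth fixing because a named estimator of the primary endpoint can be replaced, by wording alone, with one that does not depend on an unstated convention.

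**What to change.** In Sections 2.7.1 and 3.5.5.1:

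- Replace the Kaplan-Meier estimate with an Aalen-Johansen cumulative incidence of response. Competing events are death, new anticancer therapy and progression without prior response, using RECIST 1.1 progression for the primary measure.
- For irRC, keep patients without a response at risk to their data-cutoff date. Absent loss to follow-up, this estimates the same quantity. It also avoids choosing a progression event when Section 3.3.1.3 allows treatment beyond confirmed progression and Appendix 6.5 dates progression to the first scan.
- Censor only for follow-up still running at cutoff or, under Aalen-Johansen, for true loss to follow-up.
- Report the estimate with a confidence interval and the number at risk, labelled as supportive of the crude FAS RR.

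The cost is SAP wording and a standard procedure. The supplementary figure will be less favourable than a censored Kaplan-Meier figure and less precise than the crude RR: in the 115-patient simulation the standard error was 3.6 to 4.3 points against 3.2 to 3.7. The kept-at-risk version will read somewhat low if patients are truly lost.

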3.5.5.2 Pharmacokinetic Analysis

Pembrolizumab (MK-3475) PK variables (e.g., C_{max} , T_{max} , C_{trough} , and AUC) will be calculated as appropriate and summary statistics will be provided. Graphical, non-compartmental, and potentially exploratory compartmental analysis will be used for the analysis of the PK data. An exploratory analysis of a potential relationship between dose level, PK variables and clinical safety, and anti-tumor activity will be performed as appropriate.

Note: As of Amendment 11, pharmacokinetic analyses will not be performed (see Section 3.3.2).

3.5.5.3 Pharmacodynamic Analysis

Summary statistics will be provided for PD-1 receptor occupancy and PD-1 target modulation. An exploratory analysis of a potential PK-PD relationship will be performed as appropriate.

Note: As of Amendment 11, PK analyses will not be performed (see Section 3.3.2).

3.5.5.4 Predictive Biomarker Analyses

MEL Patients

To address the primary predictive biomarker hypothesis in the MEL population, the following two-step approach will be implemented: 1) estimation of a cutoff point for PD-L1 expression level based on a training set of melanoma patients, and 2) application of the cutoff point to prospectively test the biomarker hypothesis (i.e., formal validation of the cutoff point). The training set consists of patients from the cohort B enrolled through Amendment 04, including 20 ipilimumab-naïve patients at 2 mg Q3, 22 ipilimumab-naïve patients at 10 mg Q3, 41 ipilimumab-naïve patients at 10 mg Q2, 32 ipilimumab-treated patients at 10 mg Q3, and 16 ipilimumab-treated patients at 10 mg Q2. Once the cutoff point is estimated, it will be applied to the analysis of randomized patients in Part B and Part D.

The cutoff point determination process is blinded to the validation analyses to ensure they have the necessary scientific rigor and integrity to confirm a clinical benefit of pembrolizumab (MK-3475) in the "biomarker positive" patients.

Estimation of cutoff point

All patients in the training set are required to have new biopsies such that we expect the yield of tumor samples available for PD-L1 analysis to be very close to the number of patients enrolled. All tumors will be tested retrospectively, with the test operators blinded to all clinical data. Four scoring systems will be evaluated initially: one based on H-score, the other three based on the percentage of tumor cells expressing PD-L1 with minimum intensities of 1+, 2+, and 3+, respectively. The latter two scoring systems (percentage of tumor cells with minimum intensities of 2+ or 3+) may be abandoned if the operators determine that they are too difficult to score.

Kendall's tau statistic along with a one-sided p-value will be provided for testing the concordance between maximum total tumor volume reduction (%) produced by pembrolizumab (MK-3475) and PD-L1 expression levels in tumor tissue [20]. Kendall's tau statistic is rank based. For the supportive analysis, those without a post-treatment disease assessment (presumably mainly due to discontinuation before week 12) will be assigned a lower rank (equivalent to less tumor reduction) than those with a post-treatment disease assessment. They will further be ranked by category of reasons for discontinuation (death, disease progression by RECIST 1.1 per central review and other reasons) in ascending order, and among each category they will be ranked by time to

discontinuation, the earlier the lower. Supportive analysis will be performed assessing the concordance between response by RECIST 1.1 per central review and PD-L1 expression.

Receiver operating characteristic (ROC) analysis will be generated for each scoring system. The cutoff point will be chosen by statistical estimation of Youden Index assisted with visual inspection from the ROC. In addition, the following two confounding categorical variables will be evaluated to determine whether or not they can be used to further improve the scoring system: “stroma pattern” (presence or absence of a band mononuclear inflammatory cells expressing PD-L1, in the stroma adjacent to tumor nests) and “dendritic pattern” (presence or absence of a lattice of dendritic cells expressing PD-L1, within tumor nests). Once the final scoring system and cutoff point is chosen, it will be documented before validation can be conducted.

Validation

Tumor samples from patients in the validation sets will be sent to a third party contract research organization (CRO) for re-identification. The CRO will remove old identifying information from each sample and replace it with a new identifier. The samples will then be sent to the clinical laboratory sites for analysis. Thus, both Merck and the laboratories will be blinded to the linkage between PD-L1 test result and the clinical outcome. The third-party CRO will release the key containing the old versus new identifiers to Merck only after database lock.

Patients with PD-L1 expression level above the final cutoff point will be analyzed by dose/schedule, separately for the ipilimumab-refractory population and the ipilimumab-naïve population. Based upon current data from this trial indicating similar response rates between ipilimumab-naïve and ipilimumab-treated patients, an analysis will also be performed where the two populations are combined for a given dose/schedule or even across doses/schedules as appropriate. RR, DCR and other efficacy endpoints will all be compared by PD-L1 expression category (above or below cutoff). A multivariate logistic regression analysis will be conducted to further assess the cutoff point after adjustment of important baseline characteristics. Covariates in the regression model will include PD-L1 expression category (above cutoff, below cutoff or indeterminate), gender, age category (above or below median), ECOG performance status (0 or 1), LDH (\leq upper limit of the normal range OR $>$ upper limit of the normal range or unknown), baseline tumor volume (above or below median), number of previous systemic therapies ($<$ or \geq median) and other prognostic factors and predictive biomarkers as appropriate.

Indeterminate PD-L1 expression levels are presumed to be missing at random. Reasons of missing data will be listed and investigated. A supportive analysis will be conducted to include those patients suspected to violate the missing at random assumption. PD-L1 expressions levels for these patients will be conservatively imputed to appropriately penalize for possible informative missing data.

Part F 2L+ Patients

The randomization of the 250 2L+ patients may be stratified by PD-L1 expression level based on a preliminary cutoff point once available, mainly based on Part C data. Data based on the patients enrolled in the non-randomized portions of Part F (Amendment 06) will be pooled with Part C data, some data from Part A, and possibly data from 1L patients in Part F (Amendment 06), to determine the final cutoff point for patients with strongly positive tumors (the primary population in this cohort) using the same estimation methods as for the melanoma patients. Just like for the melanoma patients, the cutoff point is determined in isolation to the 250 patients enrolled in the randomized portion of Part F (Amendments 07 and 08) to ensure that the subgroup analysis of the patients with strongly positive tumors is blinded to the determination process. Notice that the cutoff point is driven by patients on the Q3W schedule. To properly compare the difference (if any) in cutoff point between the two dose schedules, patients treated at 10 mg/kg Q2W will be divided into two sets with half in the training set and half in the validation set for estimation and validation of a cutoff point specifically for the Q2W schedule.

Enrollment of patients with weakly positive tumors will be capped at 50%. Besides, an interim analysis will be conducted to potentially exclude patients with weakly positive tumors (based on final cutoff point) from further enrollment (see Section 3.5.9 for details). Regardless, the final cutoff point, once determined, won't be changed for the primary analysis purposes to maintain the integrity of the analysis.

